### 4.4.1 Full or Partial Dose

A full or partial dose is determined by clinical pharmacology and medical teams. If all treated subjects receive at least one full dose of study drug, then the Efficacy Population and the Safety Population will be the same.

A full dose of study drug is defined as a dose taken on a given day as confirmed by Dose Admin Form with the following criteria from the palatability questionnaire:

• *A "Yes" answer to "Successfully swallowed the medicine without vomiting within 2 minutes of swallowing"* 

AND

• Absence of a "Yes" answer to "Spit out or coughed it out"

AND

• Absence of a "Yes" answer to Gagged or vomited (within 2 minutes of swallowing medicine)

A partial dose of study drug is defined as a dose taken on a given day with the following criteria from the palatability questionnaire:

• *A "No" answer to "Successfully swallowed the medicine without vomiting within 2 minutes of swallowing"* 

OR

• A "Yes" answer to "Spit it out or coughed it out"

OR

• A "Yes" answer to "Gagged or vomited (within 2 minutes of swallowing medicine"

### 4.5 Analysis Visit Windows

Study day is defined as the number of days from the date of first dose. Day 1 is the date of first dose. For assessments or events after the first dose date, study day is calculated as the date of interest minus first dose date plus 1 day. For assessments/events before the first dose date, study day is calculated as the date of interest minus first dose date.

Analysis visit windows are described in the tables below.

For vital signs, safety laboratory tests, Professional ReSVinet, and RSV RNA quantitation of viral load:

Analysis Visit #	Analysis Visit Label	Target Day	Derivation	Visit Window
1	Day 1	1	Based on nominal visit	
3	Day 3	3	Based on date of assessment	2 to 4*

5	Day 5	5	Based on date of assessment	4 to 6*
9	Day 9	9	Based on date of assessment	8 to 11
14	Day 14	14	Based on date of assessment	12 to 16

\*The visit on Day 4 should be mapped to analysis Visit #3 unless there is an earlier analysis Visit #3.

For eCOA eDiary (Parent/Guardian Resvinet, Palatability Questionnaire), RESOLVE-	For eCOA eDiary	r (Parent/Guardian Re	SVinet, Palatability	Questionnaire),	, RESOLVE-P
--	-----------------	----------------------------------	----------------------	-----------------	-------------

Analysis Visit #	Analysis Visit Label	Target Day	Timepoint* Assessment	Derivation
1	Day 1	1	AM	Study day =1
1	Day 1	1	PM	Study day =1
2	Day 2	2	AM	Study day =2
2	Day 2	2	PM	Study day =2
3	Day 3	3	AM	Study day =3
3	Day 3	3	PM	Study day =3
4	Day 4	4	AM	Study day =4
4	Day 4	4	PM	Study day =4
5	Day 5	5	AM	Study day =5
5	Day 5	5	PM	Study day =5
6	Day 6	6	AM	Study day =6
6	Day 6	6	PM	Study day =6
7	Day 7	7	AM	Study day =7
7	Day 7	7	PM	Study day =7
8	Day 8	8	AM	Study day =8
8	Day 8	8	PM	Study day =8
9	Day 9	9	AM	Study day =9
9	Day 9	9	PM	Study day =9
10	Day 10	10	AM	Study day =10
10	Day 10	10	PM	Study day =10
11	Day 11	11	AM	Study day =11

11	Day 11	11	РМ	Study day =11
12	Day 12	12	AM	Study day =12
12	Day 12	12	РМ	Study day =12
13	Day 13	13	AM	Study day =13
13	Day 13	13	РМ	Study day =13
14	Day 14	14	AM	Study day =14
14	Day 14	14	PM	Study day =14

\* The ReSVinet assessments will be completed predose QD each day, by subjects' parent(s)/guardian(s), through Day 14 and at approximately the same time each day ±2 hours. The palatability question will be completed as soon as possible after each dose of study drug is administered. The RESOLVE-P assessments will be completed twice daily (AM and PM), approximately every 12 hours for 14 days. The D1 assessment must be completed pre-dose. Only one D1 assessment is expected if completed in the afternoon.

### 4.6 Subject Disposition

All subjects who provided informed consent will be included in a summary of subject accountability. The number and percentage of randomized, treated, randomized and not treated, as well as the number and percentage of subjects in each analysis population will be summarized using all subjects randomized. The denominator for the calculation of percentages will be from the number of subjects randomized.

The following categories will also be summarized by all randomized subjects:

- Completed study drug per protocol
- Discontinued study drug early and the primary reason for discontinuation
- Completed the study per protocol
- Discontinued from the study early and the primary reason for discontinuation

The number of subjects excluded from analysis sets and reasons for exclusion will be summarized.

A separate listing will be also provided for subject disposition.

# 4.7 **Protocol Deviations**

All protocol deviations (PDs) will be entered and tracked in Clinical Trial Management System (CTMS) by the study steam throughout the conduct of the study in accordance with Protocol Deviation Guidance document. Protocol deviations that adversely affect the risk/benefit ratio of the study, the rights, safety, or welfare of the participants or others, or the integrity of the study must be reported to the medical monitoring team.

The PDs will be reviewed prior to closure of the database and unblinding the study to ensure all significant deviations (classified as "Important" in the PD Guidance document) are captured and categorised.

Significant protocol deviations will be summarized. Separate listings will also be provided for significant and non-significant protocol deviations. Summaries will be conducted on all subjects who were randomized.

# 4.8 Demographic and Baseline Characteristics

No statistical testing will be performed for the comparison between treatment groups on demographics and baseline characteristics. Subject demographics and baseline characteristics will be summarized descriptively using the Safety Population.

Age, Gestational Age, Body Length, Head Circumference, and Weight, RSV viral load measured by RT-qPCR (log10 copies/mL), professional and parent/guardian ReSVinet total scores, RESOLVE-P domain and composite scores, CaGI-S total score collected at baseline, and duration of RSV symptom onset (from the first sign of respiratory infection to randomization) will be summarized.

Qualitative variables such as sex, ethnicity, race, RSV type (RSV-A, RSV-B), and pathogen will be summarized using descriptive statistics. A by-subject listing will be provided.

# 4.9 Medical History

Medical history will be coded using Medical Dictionary for Regulatory Activities (MedDRA) Version 26.1 or higher. The number and percentage of subjects with relevant medical history will be summarized by system organ class (SOC) and preferred term (PT). The percentage will be calculated based on the Safety Population. A by-subject listing will be provided.

# 4.10 Prior and Concomitant Medications

Medications used in this study will be coded using the latest available version of the World Health Organization Drug Dictionary Global B3 September 2020 or higher. Prior medications are defined as those medications with a start date prior to the first dose of study drug. Concomitant medications are defined as those medications with a start date on or after the first dose of study drug. A medication which started prior to dosing and continued after dosing will also be considered as concomitant medications. Concomitant medications will be summarized descriptively using frequency tables by Anatomical Therapeutic Chemical (ATC) level 2 (therapeutic main group) and ATC level 4 (chemical/therapeutic subgroup) and PT using the Safety Population. A by-subject listing will be provided for prior and concomitant medications. Details for imputing missing or partial start and/or stop dates of medication are described in *Section 4.3.1*.

# 4.11 Extent of Exposure

Duration of study drug (in days) will be calculated as: last dose date – first dose date + 1 day, regardless of study drug interruption. Study drug exposure will be summarized using the Safety Population and the Efficacy Population. Only the summaries of Safety Population will be provided if the Safety Population and the Efficacy Population are identical.

# 4.12 Treatment Compliance

Study drug compliance based on the number of syringes taken will be calculated as: 100 x (total number of days dosed)/ (number of days of treatment planned per protocol) except for subjects who discontinued study during the treatment period. The number of days dosed (for subjects who were lost to follow-up) or the number of days since first dose to the day of drug refusal (for subjects who refused to take study drug) is used as the denominator. Study drug compliance will be summarized using the Safety Population and the Efficacy Population. Only the summaries of Safety Population will be provided if the Safety Population and the Efficacy Population are identical.

# 4.13 Efficacy Analyses

All efficacy analyses will be based on the Efficacy Population. Selected efficacy endpoints will also be based on the mITT-3 and mITT-5 populations. Part 1 data and Part 2 data will be summarized separately using descriptive statistics. In addition, all secondary efficacy endpoints in Part 2 as well as all exploratory endpoints will be summarized based on pooled data from both Parts 1 and 2. Inferential statistical analysis will be performed to these pooled analyses, as appropriate.

# 4.13.1 Primary Efficacy Analysis Part 1

Not applicable because the primary endpoint for this part of the study is the PK analysis (please refer to *Section 4.15.1*)

# 4.13.2 Secondary Efficacy Analysis Part 1

The following secondary endpoints will be analyzed descriptively using the Efficacy, mITT-3, mITT-5 Populations.

• AUC for RSV RNA viral load measured in nasal swab samples by quantitative reverse transcription polymerase chain reaction (RT-qPCR)

RSV RNA viral load will be measured in nasal swab samples by RT-qPCR on Days 1, 3, 5, 9 and 14. Viral load values reported as TD (Target Detected, but below LLOQ) will be set to the average of LOD (limit of detection) and LLOQ (lower limit of quantification). Viral load values reported as TND (Target Not Detected, below LOD) will be set to zero. Viral load data will be transformed using a log10 scale before analyses. In case of zero value, the log transformed value will be also set as zero. For the RT-qPCR assay used for detection and quantification of RSV A and RSV B, the LLOQ is 1000 copies/mL for RSV A and 250 copies/mL for RSV B; the LOD is 620 copies/mL for RSV A and 80 copies/mL for RSV B.

The RSV type of each subject will be decided at baseline based on the RT-qPCR test. The baseline RSV viral load result is from the nasopharyngeal swab sample taken after randomization and prior to first dose on Day 1. After the imputation of TD, TND, and log10 transformation, if the baseline RSV A viral load is greater than RSV B viral load, the baseline

RSV type is classified as RSV A. Further, if the baseline RSV B viral load is greater than RSV A viral load, the baseline RSV type is classified as RSV B.

The RSV RNA viral load AUC will be calculated using the trapezoid rule [2]. The AUC will require at least 2 non-missing data points. Subjects with missing or undetectable RSV RNA viral load at baseline will be excluded from the analysis. The AUC will be calculated based on all available assessments collected on Days 1/Baseline, 3, 5, 9, and 14 and the actual date/time of each assessment will be used for the calculation. For the baseline viral load (Day 1), time is set as 0. For each assessment post first dose, the actual time in days is computed as difference between the date/time of the assessment and the date/time of the first dose. The AUC is also standardized for 14 days by multiplying 14/tlast where tlast is the actual time in days of the last available assessment. Additionally, the AUC from Day 1 through Day 3, the AUC from Day 1 through Day 5, and the AUC from Day 1 through Day 9 will be also derived and standardized similarly as for AUC from Day 1 though Day 14.

Descriptive statistics for RSV RNA viral load AUC will include, at a minimum, the number of non-missing measurements, mean, standard deviation, median, minimum, 25th percentile, 75th percentile, maximum, and 95% CI for the mean.

- Daily change in RSV shedding in nasal swab samples determined using RT-qPCR from baseline through the treatment phase
  - RSV RNA viral load observed and change from baseline will be summarized by visit (Baseline, Days 3, 5, 9 and 14). The summary statistics will include, at a minimum, the number of non-missing measurements, mean, standard deviation, median, minimum, 25th percentile, 75th percentile, maximum, and 95% CI for the mean.

Line graph of RSV RNA viral load will be produced:

- (1) Observed mean viral load  $\pm$  95% confidence interval by days (1, 3, 5, 9 and 14) for each treatment group and age group.
- Time to RSV RNA viral load being undetectable

Time to RSV RNA viral load being undetectable (TND) will be analyzed using two approaches as defined below:

- Time to RSV RNA viral load being undetectable (days) is defined as the time between the date of first dose to the first date during post-dose period of achieving RSV RNA viral load TND after which no further samples have detectable RSV RNA viral load. Subjects with baseline RSV viral load TND will be excluded from the analysis.
- Time to confirmed undetectable RSV RNA viral load (days) is defined as the time between the date of first dose to the first of 2 consecutive post-baseline time points of achieving RSV RNA viral load TND. Subjects with baseline RSV viral load TND will be excluded from the analysis.
- Proportion of subjects with RSV RNA viral load below the LOD in subjects receiving EDP-938 compared to placebo

 Frequency counts and percentages of subjects with RSV RNA viral load below the LOD will be summarized by Day 14. The respective 95% CIs will be reported using Clopper Pearson CI methods.

# 4.13.3 Primary Efficacy Analysis Part 2

- Daily change in RSV shedding in nasal swab samples determined using RT-qPCR from baseline through the treatment phase
  - RSV RNA viral load observed and change from baseline will be summarized descriptively by visit (Baseline, Days 3, 5, 9 and 14) using the efficacy, mIIT-3 and mITT-5 populations. The summary statistics will include, at a minimum, the number of non-missing measurements, mean, standard deviation, median, minimum, 25th percentile, 75th percentile, maximum, and 95% CI for the mean.

Line graph of RSV RNA viral load will be produced:

(1) Observed mean viral load ± 95% confidence interval by Days (1, 3, 5, 9 and 14) for each treatment group and age group.

# 4.13.4 Secondary Efficacy Analysis Part 2

The following efficacy analyses will be summarized using the Efficacy, mITT-3, and mITT-5 populations.

- AUC for RSV RNA viral load measured in nasal swab samples by quantitative reverse transcription polymerase chain reaction (RT-qPCR)
  - The RSV RNA viral load AUC will be summarized as described in *Section 4.13.2*.
- Proportion of subjects with RSV RNA viral load below the LOD in subjects receiving EDP-938 compared to placebo
  - Frequency counts and percentages of subjects with RSV RNA viral load below LOD will be summarized by Day 14. The respective 95% CIs will be reported using Clopper Pearson CI methods.
- Time to RSV RNA viral load being undetectable

Time to RSV RNA viral load being undetectable (TND) will be analyzed using two approaches as defined below:

- Time to RSV RNA viral load being undetectable (days) is defined as the time between the date of first dose to the first date during the post-dose period of achieving viral load TND after which no further samples have detectable RSV RNA viral load. Subjects with baseline RSV viral load TND will be excluded from the analysis.
- Time to confirmed undetectable RSV RNA viral load (days) is defined as the time between the date of first dose to the first 2 consecutive post-baseline time points of

achieving RSV RNA viral load TND. Subjects with baseline RSV viral load TND will be excluded from the analysis.

Frequency counts and percentages of subjects by end of study (Day  $28 \pm 4$ ), and their respective 95% CIs will be reported using Clopper Pearson CI methods for the following endpoints summarized using the Efficacy Population.

- Proportion of hospitalized subjects requiring oxygen supplementation or have an increased oxygen requirement.
  - Subjects who are hospitalized at randomization and/or during study are included. The
    proportion will be defined by the number of subjects who develop a new requirement for
    oxygen supplementation or new increase(s) in oxygen requirements after the first dose of
    study drug, based on the response of "yes" to the "is this an increase of oxygen
    supplementation compared to previous use?" question on the Oxygen Supplementation
    CRF.
- Proportion of hospitalized subjects requiring mechanical ventilation
  - Subjects who are hospitalized at randomization and/or during study are included. The proportion will be defined by the number of subjects who developed a new requirement for mechanical ventilation after the first dose of study drug. Subjects on mechanical ventilation prior to the first dose of study drug are excluded from analysis.
- Deaths among hospitalized subjects
  - Subjects who are hospitalized at randomization and/or during study are included.
- Proportion of outpatients who are subsequently hospitalized or died
  - $\circ$  Subjects who are not hospitalized at randomization are included.
- Proportion of outpatients who died
  - Subjects who are not hospitalized at randomization are included.

The following endpoints will be summarized using the Efficacy Population. The summary statistics will include, at a minimum, the number of non-missing measurements, mean, standard deviation, median, minimum, 25th percentile, 75th percentile, and maximum.

- Time to discharge for hospitalized subjects
  - Time to first hospital discharge for subjects who are hospitalized at randomization will be defined as the time between the first dose of study drug and the first date of discharge. For subjects with continuous hospitalization, the last date of discharge from the continuous hospitalization will be used.
- Time to use of oxygen for hospitalized subjects who are not receiving oxygen at the time they receive the first dose of study drug
  - For subjects who are hospitalized at randomization, time to use of oxygen for hospitalized subjects not receiving oxygen at the time they receive the first dose, is

defined as the time between the date/time of first dose of study drug to the first date/time of receiving oxygen.

- Duration of oxygen use for hospitalized subjects
  - This analysis will include subjects who are hospitalized at randomization and received oxygen supplementation at any time after the first dose of study drug. The duration of oxygen use (days) is defined as the sum of each duration of oxygen use (days) that occurred from the first dose of study drug to the end of study. The duration of oxygen use for the initial hospitalization is calculated as date/time of the end of oxygen use – date/time of first dose of study drug. The duration of oxygen use for subsequent rehospitalization(s) is calculated as date/time of the end of oxygen use – date/time of the start of oxygen use for the rehospitalization. Missing start times will be imputed to 00:01. Missing end times will be imputed to 23:59.
- Time to mechanical ventilation for hospitalized subjects
  - This analysis will include subjects who are hospitalized at randomization and required mechanical ventilation at any time after the first dose of study drug. Subjects on mechanical ventilation before their first dose of study drug are excluded from analysis. Time to mechanical ventilation is defined as the date/time from the first dose of study drug to the first use of mechanical ventilation.
- Duration of mechanical ventilation for hospitalized subjects
  - This analysis includes subjects who are hospitalized at randomization and required mechanical ventilation at any time after the first dose of study drug. The duration of mechanical ventilation (days) is defined as the sum of each duration of mechanical ventilation (days) that occurred from the first dose of study drug to the end of study. The duration of mechanical ventilation for the initial hospitalization is calculated as date/time of the end of mechanical ventilation date/time of first dose of study drug. The duration of mechanical ventilation for subsequent rehospitalization(s) is calculated as date/time of the end of mechanical ventilation date/time of the start of mechanical ventilation. Missing start times will be imputed to 00:01. Missing end times will be imputed to 23:59.
- Time to hospitalization for initial outpatients who are subsequently hospitalized
  - Time to hospitalization for initial outpatients who are subsequently hospitalized will be calculated, defined as the time between the date/time of first dose to the first date of hospitalization.
- Time to resolution of symptoms for outpatients who are not hospitalized
  - Time to resolution of symptoms for outpatients at randomization who are not hospitalized during study, is defined as the time between the date/time of first dose to the first of 2 consecutive time points where each of the seven symptoms assessed by the Parent/Caregiver ReSVinet clinical scoring is 0 or 1. If a subject meets the resolution

definition (0 or 1 score for 2 consecutive timepoints) at baseline and Day 2, then this subject will be excluded from the analysis.

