# **Secondary Endpoints**

- AUC for RSV RNA viral load measured in nasal swab samples by quantitative reverse transcription polymerase chain reaction (RT-qPCR)
- Daily change in RSV shedding in nasal swab samples determined using RT-qPCR from Baseline through the treatment phase
- Proportion of subjects with RSV RNA viral load below the limit of detection (LOD) in subjects receiving EDP-938 compared to placebo
- Time to RSV RNA viral load being undetectable

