# Secondary Endpoints

• Safety and tolerability of EDP-938 compared to placebo as assessed by, but not limited to, AEs, vital signs, and clinical laboratory results;

- AUC for RSV RNA viral load measured in nasal swab samples by RT-qPCR;
- Proportion of subjects with RSV RNA viral load below the LOD in subjects receiving EDP-938 compared to placebo;
- Time to RSV RNA viral load being undetectable;
- PK parameters of EDP-938 including AUC and predose concentrations;
- Time to discharge for hospitalized subjects;
- Time to use of oxygen for hospitalized subjects who are not receiving oxygen at the time they receive the first dose of study drug;
- Proportion of hospitalized subjects requiring oxygen supplementation or have an increased oxygen requirement;
- Time to mechanical ventilation for hospitalized subjects;
- Proportion of hospitalized subjects requiring mechanical ventilation;
- Deaths among hospitalized subjects;
- Time to hospitalization for initial outpatients who are subsequently hospitalized;
- Proportion of outpatients who are subsequently hospitalized or died;
- Time to resolution of symptoms for outpatients who are not hospitalized.

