# 4.13.5 Efficacy Analysis for Pooled Population

The primary endpoint is the daily change in RSV shedding in nasal swab samples determined using RTqPCR from baseline through the treatment phase in the pooled population (subjects from Parts 1 and 2 together).

All secondary efficacy endpoints described in *Section 4.13.4*, as well as all exploratory endpoints described in Section 4.13.7 are also the secondary and exploratory endpoints for the pooled population and will be analyzed with the pooled data from both Parts 1 and 2.

All pooled efficacy data will be summarized descriptively by EDP 938 and Placebo for each age group and combined EDP 938 and Placebo, as described in *Section 4.13.4* and *Section 4.13.7*.

Inferential statistics analysis will be performed to detect treatment effects of EDP 938 and Placebo using the Efficacy Population, mITT-3 and mITT-5 for the following RSV RNA viral endpoints as well as RSV symptom related endpoints described in *Section 4.13.7* (except for RESOLVE-P where Efficacy Population is used)

- Daily change in RSV shedding in nasal swab samples determined using RT-qPCR from baseline through treatment phase
  - Absolute change from baseline in RSV RNA viral load (outcome variable) will also be analyzed using MMRM as described below.
  - AUC for RSV RNA viral load measured in nasal swab samples by quantitative reverse transcription polymerase chain reaction (RT-qPCR) will be estimated via MMRM.
- Time to RSV RNA viral load being undetectable

Time to RSV RNA viral load being undetectable (TND) will be analyzed using two approaches as defined below:

- Time to RSV RNA viral load being undetectable (days) is defined as the time between the date of first dose to the first date during post-dose period of achieving RSV RNA viral load TND after which no further samples have detectable RSV RNA viral load. Subjects with baseline RSV viral load TND will be excluded from the analysis.
- Time to confirmed undetectable RSV RNA viral load (days) is defined as the time between the date of first dose to the first of 2 consecutive post-baseline time points of achieving RSV RNA viral load TND. Subjects with baseline RSV viral load TND will be excluded from the analysis.

Inferential statistics analysis approaches are as follows:

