# For continuous endpoints with multiple timepoints:

Absolute change from baseline in the outcome of interest (outcome variable) will be analyzed using a mixed-effect model for repeated measures (MMRM) to compare EDP-938 and Placebo.

The model includes treatment group (EDP-938, placebo) and Day (all scheduled post-baseline timepoints available) as fixed effect, associated baseline (as appropriate), and treatment group-by-Day interaction term as factors. Treatment groups will be compared at scheduled post-baseline timepoints of interest. An unstructured covariance matrix will be imposed. If the unstructured covariance matrix fails to converge, then the following covariance structure will be assessed in this order: autoregressive, compound symmetry, Toeplitz. The Satterthwaite approximation will be used to estimate the denominator degrees of freedom. The least-squares means and two-sided 95% CIs of absolute change from baseline at each post-baseline timepoint will be derived via this model. The least-squares means and two-sided 95% CIs of AUC through Days 3, 5, 9 and 14 will be presented for individual groups and the difference between groups. The p-value will be presented for the difference between treatment groups at each post-baseline timepoint.

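### The proportion below the LOD is defined as a comparison with placebo, but the SAP plans only separate per-arm intervals and no interval for the difference

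*SAP*

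**What the plan says.** - **Endpoint.** SAP 3.2.1 (Part 1) lists "Proportion of subjects with RSV RNA viral load below the limit of detection (LOD) in subjects receiving EDP-938 compared to placebo". SAP 3.2.2 (Part 2 and pooled population) repeats it: "Proportion of subjects with RSV RNA viral load below the LOD in subjects receiving EDP-938 compared to placebo".
- **Analysis by part.** SAP 4.13.4 says: "Frequency counts and percentages of subjects with RSV RNA viral load below LOD will be summarized by Day 14". It continues: "The respective 95% CIs will be reported using Clopper Pearson CI methods". SAP 4.13.2 says the same for Part 1.
- **Pooled description.** SAP 4.13.5: "All pooled efficacy data will be summarized descriptively by EDP 938 and Placebo for each age group".
- **Pooled inference.** SAP 4.13.5 then says: "Inferential statistics analysis will be performed to detect treatment effects of EDP 938 and Placebo using the Efficacy Population, mITT-3 and mITT-5". The viral endpoints listed under it are daily change in viral load, viral load AUC (both by MMRM) and two definitions of time to undetectable RNA. Symptom endpoints are included by reference to 4.13.7. The proportion below the LOD is not listed.
- **Inferential methods.** One block is headed "For continuous endpoints with multiple timepoints" and the other covers times to event. There is no block for binary endpoints.
- **General clause.** The opening of SAP 4.13 allows inferential analysis of the pooled endpoints where fitting, without naming a method.
- **Status of the trial.** Protocol 11.2 and 11.7 and SAP 4.2 declare the analysis descriptive, with no formal hypothesis test and no formal sample-size justification.

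**The concern.** The endpoint is worded as a contrast between arms, but the interval method attached to it describes one arm at a time. Two Clopper-Pearson intervals do not give the uncertainty of the difference. They can overlap when a proper interval for the difference excludes zero.

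The other RSV RNA secondary endpoints do get a planned comparison in the pooled population. Change and AUC get least-squares mean differences with 95% intervals, and time to undetectable RNA gets a rank test with Kaplan-Meier estimates. This endpoint is left out without a stated reason.

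It is also an endpoint on which a comparison is likely to be sought. Protocol 1.4 reports that in the study of naturally infected adults (EDP 938-102) the secondary antiviral endpoints were not met, but the percentage with undetectable RNA differed at Day 5 (p=0.033). If no estimator is fixed beforehand, any interval for the paediatric difference will rest on a later choice of method, time point and pooling rule.

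**Working it through.** **1. Planned numbers.** From SAP 2.2 and 4.2:
- Part 1: 2 cohorts × 2 age groups × 12 = 48. Cohort 1 splits 8:4. The same split is assumed for Cohort 2, in line with the 2:1 ratio. This gives 32 EDP-938 and 16 placebo.
- Part 2: 2 age groups × 20 = 40, split 16:4 in each. This gives 32 EDP-938 and 8 placebo.
- Pooled: 88 subjects, 64 EDP-938 and 24 placebo. This agrees with the stated total of approximately 90.

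**2. Per-arm interval (as planned).** Clopper-Pearson for x of n: the lower limit is the 0.025 quantile of Beta(x, n−x+1) and the upper limit is the 0.975 quantile of Beta(x+1, n−x).

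**3. Interval for the difference (not planned).** Miettinen-Nurminen: all t with |z(t)| ≤ 1.96, where

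z(t) = (p̂E − p̂P − t) / √{[p̃E(1−p̃E)/nE + p̃P(1−p̃P)/nP] × N/(N−1)}

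and p̃E, p̃P are the maximum-likelihood estimates under p̃E − p̃P = t, with N = nE + nP.

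**4. Results.** The documents give no expected proportions, so all the rates below are assumptions. The intervals are unstratified.

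| EDP-938 vs placebo | Per-arm 95% CIs | Difference | Miettinen-Nurminen 95% CI |
|---|---|---|---|
| 48/64 vs 12/24 | 62.6–85.0%; 29.1–70.9% | 25.0 points | 2.8 to 46.4 |
| 32/64 vs 6/24 | 37.2–62.8%; 9.8–46.7% | 25.0 points | 1.7 to 43.6 |
| 42/64 vs 12/24 | 52.7–77.1%; 29.1–70.9% | 15.6 points | about -7.0 to 37.7 |
| 26/64 vs 6/24 | 28.5–53.6%; 9.8–46.7% | 15.6 points | -7.4 to 34.4 |

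The per-arm intervals overlap in all four rows, but the interval for the difference excludes zero in the first two. Newcombe intervals agree closely (3.0 to 45.6 in the first row). With 6, 8, 10 or 12 placebo responders of 24, this discordance occurs for observed differences from about 23 points up to 31 to 34 points.

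For Part 2 alone, 24/32 versus 4/8 gives -9.1 to 57.7. Even a 25-point difference is not resolved there.

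**5. Why the pooled difference should be stratified by Part.** Allocation is 2:1 in Part 1 and 4:1 in Part 2, and the symptom window is 7 versus 5 days (Protocol 3.1). Suppose the drug has no effect, with 60% below the LOD in Part 1 and 40% in Part 2 (assumed):
- EDP-938: (32×0.60 + 32×0.40)/64 = 50.0%
- Placebo: (16×0.60 + 8×0.40)/24 = 53.3%
- Crude difference: -3.3 points

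At 70% and 40% it is 55.0% − 60.0% = -5.0 points. If the two parts' rates were swapped, the sign would reverse. Mantel-Haenszel weights nE·nP/(nE+nP) are 32×16/48 = 10.67 and 32×8/40 = 6.40. They average the two within-part differences, both zero here, and so return zero.

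**The case against.** The strongest defence is that the trial is declared descriptive. Every binary efficacy endpoint visible in SAP 4.13.4 gets the same per-arm treatment, which looks like a consistent choice. The general clause in 4.13 leaves room for pooled inference, and viral clearance is already compared between arms through time to undetectable RNA. The pooled analysis already spans several endpoints, up to three populations and several days, so one more contrast adds to multiplicity. The table shells are a separate document, and SAP 4.13.7 is not in the available text.

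Much of this stands, and it rules out stronger readings that a reader might infer:
- **That the comparison cannot be made at all.** Both percentages are reported by arm, so the crude difference is a subtraction, and 4.13 does not forbid more. What is missing is a named estimator and its interval.
- **That the plan tells readers to judge by overlapping intervals.** Neither document proposes that rule. Overlap is only a foreseeable misuse of what will be shown.
- **That the adult result concerned the same quantity.** That result was at Day 5, while the SAP tabulates this endpoint by Day 14.
- **That a formal test is missing.** None is promised for this endpoint.

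The defence does not remove the gap. The descriptive label did not stop the sponsor planning differences, intervals and p-values for the sibling viral endpoints in the same pooled population. Time to undetectable RNA is a different estimand, and Kaplan-Meier curves with rank tests do not yield a difference in proportions with an interval. SAP 4.13.5 cites 4.13.7 only for exploratory and symptom endpoints, so that section is unlikely to fill the gap. Multiplicity is a reason to label the result as estimation, not to leave its uncertainty unreported.

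**Conclusion.** The point holds in a limited form. For the one RSV RNA secondary endpoint left off the pooled between-arm list, the SAP states a method that cannot quantify the uncertainty of the contrast in the endpoint's own definition, and it gives no binary method elsewhere in the available text. It should be corrected, but it does not threaten the primary analysis.

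On size: at 64 versus 24, an observed 25-point difference can go with overlapping per-arm intervals and an interval for the difference that just excludes zero. A 15.6-point difference leaves an interval spanning zero. An added interval would therefore often be wide, and reporting that width is part of its value. Ignoring Part could shift the crude difference by 3 to 5 points under the assumed rates.

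This rests on the assumed 8:4 split in Cohort 2, full enrolment with complete swabs, and response rates chosen for illustration.

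**What to change.** - Add the proportion below the LOD to the pooled list in SAP 4.13.5.
- Report the EDP-938 minus placebo risk difference with a 95% interval (Miettinen-Nurminen or Newcombe), stratified at least by Part, and by age group where the small placebo cells allow. In Part 2 each age group has 4 planned placebo subjects.
- Report it at Day 5 (end of treatment), to match the timing of the adult result, and at Day 14.
- State whether the Day 14 summary means at that visit or at any time up to it, and how missing swabs count in the denominator.
- Label the result as an estimate without a formal test.
- Keep the per-arm Clopper-Pearson intervals as description.

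The cost is a few sentences in the SAP and an extra table column at two time points. Swabs are already scheduled on both days, so no new data are needed. Protocol 11.2 allows changes in the SAP only before unblinding, so this must be settled by then.
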